9.6.2.2 Evening Dose of Study Drug

If a subject misses the evening dose of IVA and recalls within 6 hours, the subject should take his/her dose with food. If more than 6 hours have elapsed after his/her usual dosing time, the subject should skip that dose and resume his/her normal schedule for the following dose.

9.7 Dose Modification for Toxicity

No dose modifications for toxicity are allowed. Treatment may be interrupted as outlined in Section 9.8. If any unacceptable toxicity arises, individual subjects will discontinue dosing (Section 9.1.3).

9.8 Study Drug Interruption and Stopping Rules

The medical monitor should be notified of an interruption of study drug that lasts >72 hours for any reason and of the resumption of study drug after such interruption.

9.8.1 Liver Function Tests

The central laboratory will notify the medical monitor of ALT or AST $>3 \times$ ULN and total bilirubin $>2 \times$ ULN that are derived from centrally submitted samples.

Subjects with new treatment-emergent ALT or AST elevations of $>3 \times$ upper limit of normal (ULN), with or without total bilirubin $>2 \times$ ULN, must be followed closely, including confirmatory testing performed by the central laboratory within 48 to 72 hours of the initial finding and subsequent close monitoring of ALT, AST, and bilirubin levels, as clinically indicated.

If a subject cannot return to the site for confirmatory testing, a local laboratory may be used. Local laboratory results must be reported immediately to the medical monitor, and the subject must have the tests repeated and sent to the central laboratory as soon as possible (ideally within 48 to 72 hours).

Study drug administration **must be interrupted** immediately (prior to confirmatory testing) if any of the following criteria are met:

- ALT or AST $>8 \times$ ULN
- ALT or AST $>5 \times$ ULN for more than 2 weeks
- ALT or AST $>3 \times$ ULN, in association with total bilirubin $>2 \times$ ULN and/or clinical jaundice

A thorough investigation of potential causes should be conducted, and the subject should be followed closely for clinical progression.

Study drug administration **must be discontinued** if the following criterion is met:

- Subsequent ALT or AST values confirm the initial elevation that satisfied the interruption rule (above), and no convincing alternative etiology (e.g., acetaminophen use, viral hepatitis, alcohol ingestion) is identified, regardless of whether transaminase levels have improved.

All subjects in whom treatment is discontinued for elevated transaminases (and bilirubin, as applicable) should have these levels monitored closely until levels normalize or return to baseline.

If an alternative, reversible cause of transaminase elevation with or without increased bilirubin or clinical jaundice has been identified, study drug administration may be resumed once transaminases return to baseline or are $\leq 2 \times$ ULN, whichever is higher. Regardless of the duration of interruption, the medical monitor should be notified prior to resumption of study drug. Upon resumption of study drug, transaminases and bilirubin should be assessed weekly for 4 weeks. If a protocol-defined transaminase elevation interruption threshold recurs within

4 weeks of rechallenge with the study drug (with confirmation of the initial elevation by repeat testing within 48 to 72 hours), then the study drug must be permanently discontinued, regardless of the presumed etiology.

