#### **Baseline value:**

- The parent study baseline is defined as the most recent non-missing measurement (scheduled or unscheduled) collected before the first dose of study drug in the parent study (studies 102 or 103). The parent study baseline will be used to calculate the absolute and relative change from baseline for efficacy analyses unless otherwise specified.
- The TC safety baseline is defined as the most recent non-missing measurement (scheduled or unscheduled) collected before the first dose of study drug in the parent study (if the subject actually received at least one dose of VX-659/TEZ/IVA during the parent study) or the first dose of study drug in the OLS (if the subject did not actually receive at least one dose of VX-659/TEZ/IVA during the parent study). The TC safety baseline will be used in the safety analyses.

**Change (absolute change)** from baseline will be calculated as post-baseline value - baseline value.

**Unscheduled visits:** Unscheduled visit measurements will be included in analysis as follows:

- 1) In scheduled visit windows per specified visit windowing rules
- 2) In the derivation of baseline and last on-treatment measurements
- 3) In the derivation of maximum and minimum values, and maximum and minimum change from baseline values during the analysis period for the safety analyses
- 4) In individual subject data listings as appropriate

**Visit windowing rules:** The analysis visit windows for protocol-defined visits for study 105 are provided in Section 12.1. The visit window for the parent studies are described in the SAP for the individual parent studies.

**Incomplete/missing data** will not be imputed, unless specified otherwise.

**Outliers:** No formal statistical analyses will be performed to detect or remedy the presence of statistical outliers, unless specified otherwise.

**Multiplicity:** There will be no multiplicity adjustment, unless specified otherwise.

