### **9.4.2 Clinical Laboratory Assessments**

For the laboratory assessments during OL safety period, the observed values and change from TC safety baseline values of the continuous hematology, coagulation and chemistry results will be summarized in SI units at each visit.

The number and percentage of subjects meeting at least 1 threshold analysis criterion event during the OL safety period will be summarized. The threshold analysis criteria are provided in Section 12.4.

Results of positive urine/serum pregnancy test from study 105 will be presented in individual subject data listings only. For positive serum pregnancy listing, subjects with serum HCG which are abnormally high will be selected. In addition, a listing containing individual subject hematology, chemistry, and coagulation values from study 105 will be provided. This listing will include data from both scheduled and unscheduled visits. The listings will be based on OL All Subjects set.

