## 12.4 Criteria for Threshold Analysis

**Table 12-3 Threshold Analysis Criteria for Laboratory Tests**

Parameter	Threshold Analysis	Comments
Clinical Chemistry (LFT)		
ALT	>ULN - ≤3xULN >3x - ≤ 5xULN >5x - ≤ 8xULN >8x - ≤ 20xULN >20xULN	FDA DILI Guidance Jul 2009.
AST	>ULN - ≤3xULN >3x - ≤ 5xULN >5x - ≤ 8xULN >8x - ≤ 20xULN >20xULN	FDA DILI Guidance Jul 2009.
ALT or AST	(ALT>ULN - ≤ 3xULN) or (AST>ULN - ≤ 3xULN) (ALT>3x - ≤ 5xULN) or (AST>3x - ≤ 5xULN) (ALT>5x- ≤ 8xULN) or (AST>5x - ≤ 8xULN) (ALT>8x - ≤ 20xULN) or (AST>8x - ≤ 20xULN) ALT>20xULN or AST> 20 xULN	FDA DILI Guidance
Alkaline Phosphatase	>ULN - ≤ 1.5xULN >1.5 – ≤ 2.5 xULN >2.5 – ≤ 5.0 x ULN >5.0 – ≤ 20.0 x ULN >20.0 x ULN	FDA DILI Guidance Jul 2009.
Total Bilirubin	>ULN - ≤ 1.5xULN >1.5 – ≤ 2xULN >2 – ≤ 3xULN >3 – ≤ 10xULN >10xULN	FDA DILI Guidance Jul 2009.
Direct Bilirubin	>ULN - ≤ 1.5xULN >1.5 – ≤ 2xULN >2 – ≤ 3xULN >3 – ≤ 10xULN >10xULN	FDA DILI Guidance Jul 2009.
Indirect Bilirubin	>ULN - ≤ 1.5xULN >1.5 – ≤ 2xULN >2 – ≤ 3xULN >3 – ≤ 10xULN >10xULN	FDA DILI Guidance Jul 2009.
ALT and Total Bilirubin	ALT>3xULN and TBILI>2xULN	FDA DILI Guidance Jul 2009.

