**Table 12-4 Threshold Analysis Criteria for Laboratory Tests (for labeling purpose)**

Parameter	Threshold Analysis	Comments
Clinical Chemistry (LFT)		
ALT or AST	>3xULN >5xULN >8xULN	For labeling purpose

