**Table 12-5 Threshold Analysis Criteria for ECGs**

Parameter	Threshold Analysis	Comments
	Tachycardia	Per HV grade 1, 2, 3, plus shift change
	>100 bpm >115 bpm >130 bpm Increase from baseline $\geq 10$ bpm Increase from baseline $\geq 20$ bpm >100 bpm and increase from baseline $\geq 10$ bpm >100 bpm and increase from baseline $\geq 20$ bpm	
PR	$\geq 240$ ms $\geq 300$ ms $\geq 200$ ms and increase from baseline $\geq 40$ ms $\geq 200$ ms and increase from baseline $\geq 100$ ms	
QRS	>110 ms >160 ms Increase from baseline $\geq 20$ ms Increase from baseline $\geq 40$ ms	
QTc Borderline Prolonged* Additional	>450 ms and <500ms (Male); >470 ms and <500ms (Female) $\geq 500$ ms  Increase from baseline Increase from baseline >10 ms Increase from baseline >20 ms Increase from baseline >40 ms Increase from baseline >60 ms	To be applied to any kind of QT correction formula.

Note: Based on CPMP 1997 guideline.

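### The protocol's baseline-to-post-baseline shift of laboratory thresholds is missing from the visible SAP, so no planned threshold summary separates new from pre-existing abnormality

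*Protocol*

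**What the plan says.** **Protocol 12.3.4.2** plans two threshold outputs for laboratory data. One is the number and percentage of subjects with at least one threshold event in the treatment-emergent period. The other is a summary of how subjects shift on the threshold criteria between baseline and post-baseline, for selected parameters. The criteria and the parameter selection were to be given in the SAP.

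**SAP 9.4.2** carries over the first: "The number and percentage of subjects meeting at least 1 threshold analysis criterion event during the OL safety period will be summarized". It also gives by-visit observed values and changes from TC safety baseline for continuous results, and listings. Table 9-2 names two laboratory outputs, the change summary and the threshold analysis. Neither place mentions a shift or a parameter selection.

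**SAP Tables 12-3 and 12-4** set the laboratory criteria as absolute limits or multiples of ULN. The 3x to 5xULN row for the combined transaminases, for example, is ("ALT>3x - ≤ 5xULN) or (AST>3x - ≤ 5xULN"). Table 12-4 repeats ALT or AST above 3x, 5x and 8xULN, marked "for labeling purpose". No laboratory row refers to baseline. Tables 12-5 and 12-6 do use baseline for ECG, vital signs and weight, for example "Increase from baseline >60 ms".

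**SAP 9.1** defines a TC safety baseline as the last value before the first triple-combination dose, in the parent study or in Study 105 as applicable, and states: "The TC safety baseline will be used in the safety analyses".

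**Protocol 9.8.1** uses "Subjects with new treatment-emergent ALT or AST elevations of" for its rule on close follow-up and confirmatory testing.

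**The concern.** The any-value count cannot distinguish a subject who crossed a limit on triple combination from one who was already past it beforehand and was past it again at some point in the open-label safety period. The shift summary in the protocol would have made that distinction, and it does not appear in the visible SAP.

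Clinical laboratory values are part of the primary safety endpoint. SAP 9.4 pools both parent studies under a single treatment label, so there is no control column for laboratory thresholds. The possible side-by-side display with Study 102 is for AE tables only. A reader of the threshold tables, including the rows kept for labeling, could not tell what share of a percentage was present before treatment.

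**Working it through.** The plan states no figure on this point, so the main check is a comparison of texts.

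1. *Count.* Protocol 12.3.4.2 and SAP 9.4.2 agree: both count any subject with a qualifying value in the period, whatever the baseline.
2. *Shift.* It is in Protocol 12.3.4.2 and absent from SAP 9.4.2 and Table 9-2.
3. *Reason for removal.* SAP Section 3 says the amendment took out analyses that early termination made impossible. A shift needs a TC safety baseline value and the worst value in the open-label safety period. SAP 9.4.2 already uses that baseline and the on-treatment values for the change summaries, so early termination does not prevent it.
4. *Can pre-existing abnormality occur?* The exclusion criteria in Protocol 8.2 set no numeric laboratory limit. The resumption wording in 9.8.1 takes the higher of baseline and 2xULN, which allows for baselines above 2xULN. Neither shows that such subjects enrolled.

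**Illustration, all rates assumed.** The planned enrolment is over 400, so take n = 400. Let b be the share above a threshold at TC safety baseline, p the share of those above it again in the open-label period, and i the new incidence in the rest.

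- Pre-existing cases counted = n × b × p
- New cases = n × (1 − b) × i
- Pre-existing share of the count = pre-existing / (pre-existing + new)

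Example with b = 2%, p = 1, i = 5%: 400 × 0.02 × 1 = 8; 400 × 0.98 × 0.05 = 19.6; count 27.6; share 8/27.6 = 29.0%.

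| b | p | Pre-existing | New | Count | Pre-existing share |
|---|---|---|---|---|---|
| 0.5% | 0.5 | 1 | 19.9 | 20.9 | 4.8% |
| 0.5% | 1 | 2 | 19.9 | 21.9 | 9.1% |
| 1% | 0.5 | 2 | 19.8 | 21.8 | 9.2% |
| 1% | 1 | 4 | 19.8 | 23.8 | 16.8% |
| 2% | 0.5 | 4 | 19.6 | 23.6 | 16.9% |
| 2% | 1 | 8 | 19.6 | 27.6 | 29.0% |
| 5% | 0.5 | 10 | 19.0 | 29.0 | 34.5% |
| 5% | 1 | 20 | 19.0 | 39.0 | 51.3% |

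The result also depends on i. With b = 2% and p = 1, the share is 50.5% at i = 2% (8/15.84) and 16.9% at i = 10% (8/47.2). With b = 0 it is zero.

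**The case against.** A reader might infer from 9.8.1 that the protocol acts on new elevations while the SAP counts all of them, so that the two documents contradict each other. The text does not support that. The word *new* there governs follow-up and confirmatory testing only. In the same section the central-laboratory alert uses plain ULN multiples, and so do the interruption criteria, which apply "immediately (prior to confirmatory testing) if any of the following criteria are met" and do not repeat the word. On the count itself, protocol and SAP agree.

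A reader might also infer that the SAP presents pre-existing abnormality as caused by the drug. It does not. It counts subjects meeting a criterion in a period, and safety is descriptive only. An any-value count can overstate new abnormality but cannot hide it.

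Other points on this side:

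- TEAEs must be new or worsened, clinically significant worsening is recorded as an AE, and change summaries and listings are planned. This gives partial context, but none of it is a summary split at threshold level.
- Stable carry-over in the highest rows is limited, because 9.8.1 requires interruption above 8xULN, and above 5xULN for more than 2 weeks, whatever the baseline. A single qualifying value would still be counted.
- Parent-study laboratory eligibility is not in the documents, so baseline elevations above 3xULN may be rare.
- SAP text is blacked out between 9.4.7 and 9.4.9 and between 12.4 and 12.6. A shift analysis there cannot be excluded, although the visible Table 9-2 lists none.

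These points limit the size and rule out the claim of a contradiction. They do not supply the shift summary.

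**Conclusion.** The point holds as an omission. The visible SAP drops a baseline-referenced threshold summary that the protocol planned and that remains feasible. What is left does not separate new or worsened laboratory abnormality from abnormality present at TC safety baseline.

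The size cannot be derived from the documents, which give neither baseline prevalence, nor persistence, nor new incidence. The 4.8% to 51.3% range belongs to the assumed inputs (n = 400, i = 5%, b from 0.5% to 5%, p of 0.5 or 1) and is no estimate for this trial; it would be nil if nobody started above a limit. No statement that the liver rates will be too high by a given percentage is justified. The change is worth making because it is cheap and bears on the primary safety endpoint.

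**What to change.** In SAP 9.4.2 and Table 9-2:

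- Restore the shift from TC safety baseline category to worst category in the OL safety period, for at least ALT, AST, ALT or AST combined, and total bilirubin. State this as the parameter selection that Protocol 12.3.4.2 leaves to the SAP.
- Keep the any-value count. Beside it, including the three Table 12-4 labeling rows, show the number of subjects whose worst open-label category is worse than their TC safety baseline category.
- State the at-risk denominator for each row: subjects not in that or a worse category at TC safety baseline. Treat a missing baseline as not in the category.

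Because TC safety baseline precedes the first triple-combination dose, an elevation that began on triple combination in a parent study and is still present in the open-label period would still show as worsened. Keeping the any-value count means that no signal is hidden. No clinical rule changes. The cost is a short SAP addition, a flag derived from data already held, and one extra table or column. If a blacked-out section already contains the shift, a cross-reference in 9.4.2 and Table 9-2 would meet the first item.

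### The liver restart rule in Protocol Section 9.8.1 sets a transaminase limit only, so as written it allows restart while bilirubin is still >2×ULN or jaundice persists

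*Protocol*

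**What the plan says.** All the operative text is in Protocol Section 9.8.1.

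- **Interruption.** There are three criteria, each requiring an immediate stop before confirmatory testing: ALT or AST >8×ULN; ALT or AST >5×ULN for more than 2 weeks; and ALT or AST >3×ULN "in association with total bilirubin" >2×ULN and/or clinical jaundice.
- **Discontinuation.** Drug is stopped for good if repeat values confirm the elevation and "no convincing alternative etiology (e.g., acetaminophen use, viral hepatitis, alcohol ingestion) is identified, regardless of whether transaminase levels have improved".
- **Restart.** The rule applies where an "alternative, reversible cause of transaminase elevation with or without increased bilirubin or clinical jaundice has been identified, study drug administration may be resumed". The threshold follows: "study drug administration may be resumed once transaminases return to baseline or are" ≤2×ULN, whichever is higher.
- **Around restart.** Beforehand, "the medical monitor should be notified prior to resumption of study drug". Afterwards, "Upon resumption of study drug, transaminases and bilirubin should be assessed weekly for 4 weeks".
- **Rechallenge stop.** "If a protocol-defined transaminase elevation interruption threshold recurs within" 4 weeks of rechallenge, and repeat testing confirms it, the drug is permanently discontinued whatever the presumed cause.
- **Follow-up after discontinuation.** Subjects discontinued for raised transaminases, and bilirubin where applicable, "should have these levels monitored closely until levels normalize or return to baseline".

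The same section also requires close follow-up of any new treatment-emergent ALT or AST >3×ULN, whether or not bilirubin is raised. That includes confirmatory testing and later monitoring of ALT, AST and bilirubin as clinically indicated.

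**The concern.** The third criterion has two parts: a transaminase rise, and raised bilirubin or jaundice. With transaminases between 3 and 5×ULN, or between 5 and 8×ULN for no more than 2 weeks, the second part is what turns close monitoring into a mandatory stop. The restart sentence then asks only whether the first part has settled.

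Patient safety is at stake, not estimation. A subject could be re-exposed while the finding that forced the stop is still present, and the written rule would have been followed. Because the protocol gives a numeric limit for transaminases, a site may read its silence on bilirubin as meaning that no bilirubin condition applies, and sites may decide differently.

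**Working it through.** The plan gives no figure to reproduce, and no sample size, power or event rate is involved. The check sets the rules side by side and follows one subject through them.

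**Step 1: which rules can bilirubin or jaundice affect?**

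| Rule in Section 9.8.1 | Transaminase condition | Bilirubin or jaundice condition |
|---|---|---|
| Interruption 1 | >8×ULN | none |
| Interruption 2 | >5×ULN for more than 2 weeks | none |
| Interruption 3 | >3×ULN | bilirubin >2×ULN and/or jaundice, in addition |
| Restart | baseline or ≤2×ULN, whichever is higher | none |
| Rechallenge stop | an interruption threshold recurs | only as part of interruption 3 |

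Bilirubin or jaundice alone can meet 0 of the 3 interruption criteria. It follows that neither alone can meet the rechallenge stop.

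**Step 2: who reaches the restart sentence?** Only subjects with an alternative, reversible cause identified. A confirmed elevation with no convincing alternative cause leads to discontinuation. The sentence expressly includes cases with raised bilirubin or jaundice.

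**Step 3: one subject followed through (assumed values, for illustration).**

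| Time | ALT | Total bilirubin | Jaundice | Result under the written rule |
|---|---|---|---|---|
| Event; viral hepatitis identified | 4×ULN | 3×ULN | yes | Interruption 3 met (4 > 3 and 3 > 2) |
| Later | 1.8×ULN | 3×ULN | yes | Restart permitted (1.8 ≤ 2) |
| After restart, unchanged | 1.8×ULN | 3×ULN | yes | No interruption criterion met (1.8 is not > 3); rechallenge stop not met |

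**Step 4: is the missing condition supplied elsewhere?** Protocol Sections 9.7 (stop for unacceptable toxicity), 9.8 (notice of interruptions over 72 hours) and 9.9 (withdrawal at the discretion of the investigator or sponsor) add no bilirubin or jaundice condition for restart. SAP Section 12.4 tabulates bilirubin thresholds but has no restart rule.

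**Step 5: how many subjects?** Five things must coincide: interruption under the third criterion; an alternative, reversible cause; recovered transaminases; bilirubin still >2×ULN or jaundice still present; and a decision to restart. The documents give no rate for any of these. SAP Table 12-3 will count subjects with ALT or AST >3×ULN and total bilirubin >2×ULN, which covers only the laboratory part of the trigger. It does not capture jaundice, cause, interruption or restart.

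**The case against.** The strongest reply is that Section 9.8.1 already protects these subjects before restart. Close follow-up is mandatory, with bilirubin monitored as clinically indicated. The central laboratory notifies the medical monitor of ALT or AST >3×ULN and total bilirubin >2×ULN, although the wording leaves unclear whether bilirubin alone triggers the notice. Causes must be investigated and the subject followed for clinical progression. Restart is permitted rather than required, and the medical monitor should be told first. Weekly bilirubin tests follow, adverse events are queried at each study visit, and the independent data monitoring committee reviews safety regularly. This largely stands: it makes it likely that a persisting elevation is seen. It does not supply the missing condition, because none of these steps says that bilirubin or jaundice must have recovered.

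A second reply is that the protocol uses bilirubin throughout only as a qualifier to a transaminase rise, so a transaminase-based restart rule fits the design. This also stands in part. The count of 0 of 3 describes the whole scheme and is not a defect peculiar to restart. What remains is narrower: once bilirubin or jaundice has contributed to a mandatory stop, the rule does not ask whether it has gone.

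Three stronger readings are tempting, and the documents do not support them.

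- *Bilirubin goes unwatched before restart.* The close follow-up duty includes it; only the timing of tests is left to clinical judgment.
- *Section 9.8.1 contradicts itself because discontinued subjects are followed until levels normalize or reach baseline.* That is a follow-up duty, whereas the restart sentence sets a threshold. The two serve different purposes.
- *A subject with a confirmed but unexplained combined elevation could be restarted.* The discontinuation rule prevents this.

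**Conclusion.** The point holds as a gap in the written rule, at low severity. For subjects interrupted under the third criterion in whom an alternative, reversible cause is found, Section 9.8.1 permits restart with bilirubin still >2×ULN or jaundice present. Confidence in that reading is high: the restart sentence is complete in the text, and neither document adds the condition elsewhere. Confidence that it would lead to harm is not high. The subset is small, its size cannot be derived, and the existing safeguards make an unnoticed case unlikely.

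The conclusion rests on reading the restart sentence literally, and on no operating document outside the protocol and SAP supplying the condition. SAP Section 3 records a decision to end the study early, so the benefit is limited to subjects still on drug and to any later study that reuses the rule.

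**What to change.** Add to the restart sentence in Section 9.8.1:

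*For subjects interrupted for ALT or AST >3×ULN with total bilirubin >2×ULN and/or clinical jaundice, total bilirubin must also have returned to baseline or be ≤2×ULN, whichever is higher, and any new clinical jaundice must have resolved or returned to baseline, before resumption.*

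The 2×ULN value is the protocol's own trigger, and the baseline alternative mirrors the transaminase limit. Limiting the jaundice condition to new jaundice, or a return to baseline, keeps it consistent with a baseline bilirubin above 2×ULN. The sponsor's hepatic safety experts may prefer a stricter limit.

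This should be a protocol amendment. Section 13.2.3 requires investigator and sponsor approval of modifications, IRB/IEC notification before implementing changes that significantly affect safety (immediate hazards excepted), and submission to the required regulatory authorities; a site letter alone would not meet this. No new test is needed, because total and direct bilirubin are already in the chemistry panel (Table 11-1). The clinical cost is that some interruptions will last longer. The change is optional but cheap.
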